2. LIST OF ABBREVIATIONS

Term	Definition / description
ACS	Acute Coronary Syndromes
ACEF	Age, creatinine and left ventricular ejection fraction
ADS	Analysis Dataset
AE	Adverse Event
AF	Atrial Fibrillation
ALT	Alanine aminotransferase
AP	Alkaline Phosphatase
ASA	Acetylsalicylic acid (Aspirin)
AST	Aspartate transaminase
BARC	Bleeding Academic Research Consortium
BI	Boehringer Ingelheim
b.i.d.	Twice a day
BMI	Body Mass Index
BMS	Bare Metal Stent
CABG	Coronary Artery Bypass Graft
CAD	Coronary Artery Disease
CHA ₂ DS ₂ VASC	Congestive heart failure, Hypertension, Age, Diabetes mellitus, prior Stroke or TIA or Thromboembolism, Vascular disease, Sex
CI	Confidence Interval
CrCl	Creatinine Clearance
CTP	Clinical Trial Protocol
CTR	Clinical Trial Report
DAPT	Dual Antiplatelet Therapy
DAT	Dual Antithrombotic Therapy
DBL	Database Lock
DBLM	Database Lock Meeting
DES	Drug Eluting Stent
DMC	Data Monitoring Committee
DTE	Death or Thrombotic Event

Term	Definition / description
ECG	Electrocardiogram
eCRF	Electronic Case Report Form
EMA	European Agency for the Evaluation of Medicinal Products
EOT	End of Treatment
EU	European Union
FAS	Full Analysis Set
GI	Gastrointestinal
HAS-BLED	Hypertension, Abnormal renal and liver function, Stroke, Bleeding, Labile INRs, Elderly, Drugs or alcohol
HF	Heart Failure
HR	Hazard Ratio
IAC	Independent Adjudication Committee
ICH	International Conference on Harmonisation
INR	International Normalised Ratio
IPV	Important Protocol Violation
IRT	Interactive Response Technology
ISTH	International Society of Thrombosis and Haemostasis
LAD	Left Anterior Descending Coronary Artery
LM	Left Main Coronary Artery
LVEF	Left Ventricular Ejection Fraction
MBE	Major Bleeding Event
MedDRA	Medical Dictionary for Regulatory Activities
mg	milligrams
MI	Myocardial Infarction
mRS	modified Rankin Scale
NI	Non-Inferiority
NOAC	New Oral Anticoagulant
NSAID	Non-Steroidal Anti-Inflammatory Drug
NSTEMI	Non-ST Elevation Myocardial Infarction
NVAF	Non Valvular Atrial Fibrillation
NYHA	New York Heart Association

Term	Definition / description
OAC	Oral Anticoagulant
OE	Outcome Event
PCI	Percutaneous Coronary Intervention
P-gp	P-glycoprotein
PPI	Proton Pump Inhibitor
PPS	Per Protocol Set
PROBE	Prospective, Randomised, Open-label, Blinded Endpoint
PT	Preferred Term
PV	Protocol Violation
Q1	Lower quartile (25 th percentile)
Q3	Upper quartile (75 th percentile)
REP	Residual Effect Period
ROW	Rest of World
RPM	Report Planning Meeting
SCR	Screened Set
SD	Standard Deviation
SE	Systemic Embolism
SOC	System Organ Class
STEMI	ST Elevation Myocardial Infarction
TAT	Triple Antithrombotic Therapy
TIA	Transient Ischaemic Attack
TIMI	Thrombolysis In Myocardial Infarction
TS	Treated Set
TSAP	Trial Statistical Analysis Plan
TTR	Time in Therapeutic Range
UA	Unstable Angina
ULN	Upper Limit of Normal
VKA	Vitamin K Antagonist
WHO	World Health Organisation

3. INTRODUCTION

As per ICH E9 [4], the purpose of this document is to provide a more technical and detailed elaboration of the principal features of the analysis described in the protocol, and to include detailed procedures for executing the statistical analysis of the primary and secondary variables and other data.

This Trial Statistical Analysis Plan (TSAP) assumes familiarity with the Clinical Trial Protocol (CTP) [5], including Protocol Amendments. In particular, the TSAP is based on the planned analysis specification as written in CTP Section 7 “Statistical Methods and Determination of Sample Size”. Therefore, TSAP readers may consult the CTP for more background information on the study, e.g., on study objectives, study design and population, treatments, definition of measurements and variables, planning of sample size, randomization.

SAS[®] Version 9.2 (or a later version) will be used for all analyses.

4. CHANGES IN THE PLANNED ANALYSIS OF THE STUDY

During the course of the study, the DMC may advise to stop enrolment into certain treatment arms or to stop the study completely. For further information, see CTP [5], Section 7.3.4. Changes to the planned analysis were introduced in protocol amendments 1 and 2. In addition, some further changes were implemented as follows.

Due to the Japanese local amendment (where the randomisation age group stratification factor was changed from <80 or ≥80 years old to <70 or ≥70 years old for Japanese patients), it will be necessary to change the way the age group stratification factor is defined in the analysis. Instead age group will be changed to be non-elderly vs. elderly and this will be used as the stratification factor in some analyses.

Due to the relatively few numbers of elderly patients finally recruited in the US region, it will not be possible to fit an age-group stratified Cox proportional hazards regression model for the 150mg DE-DAT versus warfarin-TAT comparison for any of the endpoints. Instead an unstratified model will be applied comparing 150mg DE-DAT versus warfarin-TAT. (excluding elderly EU/ROW patients in the warfarin-TAT group). In addition, unstratified sensitivity analyses of the non-elderly stratum only will be conducted.

GI bleeds, MBEs (ISTH), CRNMBEs, life-threatening bleeds and fatal bleeds were added as other safety endpoints.

The further endpoint of hospitalisation and the further composite endpoint of all-cause death or hospitalisation were added at the request of the Executive Steering Committee on 22nd November 2016.

The sensitivity analysis that censors patients who switch from study dabigatran to non-study NOAC/VKA or from study warfarin to non-study NOAC/VKA, at the time of the switch plus the Residual Effect Period (REP) of 6 days will not be performed because it will be virtually identical to the on-treatment sensitivity analysis already planned.

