7.3 PLANNED ANALYSES

7.3.1 Primary analyses

The primary endpoint (measured from date of randomisation to end of observation period) is:

- Time to first MBE/CRNMBE

as determined by the IAC. It will be analysed using the stratified Cox proportional hazards regression model including factors for age (<80 or ≥80 years old) and treatment arm (110mg DE-DAT vs warfarin-TAT and 150mg DE-DAT vs warfarin-TAT). Models will be fitted for each comparison separately.

The primary analysis will be performed under the intention-to-treat framework on the full analysis set of patients (FAS) that includes all randomised patients (regardless of whether they have received treatment). Patients who discontinue study medication will be followed until the end of the trial. Patients who are lost to follow-up for vital status will be censored for the primary endpoint at the time of their last known vital status. All patients will be analysed according to the treatment arm to which they were randomised.

For the comparison of 110mg DE-DAT vs warfarin-TAT, patients of all ages and geographical regions will be included. For the comparison of 150mg DE-DAT vs warfarin-TAT, patients from the EU/ROW who are ≥80 years old will be excluded from the warfarin-TAT arm (as patients who are ≥80 years old from the EU/ROW are not randomised to 150mg DE-DAT).

The robustness of the primary analysis will be assessed by an on-treatment analysis. This on-treatment analysis will only count events that occur while a patient is taking study medication (including the REP of 6 days – see [Section 5.2.2.2](#)). It will also analyse patients by the actual treatment that was being taken while the event occurred.

Proprietary confidential information.

© 2016 Boehringer Ingelheim International GmbH or one or more of its affiliated companies. All rights reserved.

This document may not - in full or in part - be passed on, reproduced, published or otherwise used without prior written permission.

In addition, a sensitivity analysis will be performed that censors patients who switch from dabigatran to non-study warfarin or from study warfarin to non-study NOAC, at the time of the switch. The proportional hazards assumption will be investigated.

Kaplan-Meier curves will also be presented.

Subgroup analyses are planned and will be specified in the Trial Statistical Analysis Plan (TSAP).

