7.5 RANDOMISATION

Patients aged <80 years old will be randomly assigned to 110mg DE-DAT, 150mg DE-DAT or warfarin-TAT in a 1:1:1 ratio for the duration of the trial.

Proprietary confidential information.

© 2016 Boehringer Ingelheim International GmbH or one or more of its affiliated companies. All rights reserved.

This document may not - in full or in part - be passed on, reproduced, published or otherwise used without prior written permission.

Patients aged ≥ 80 years old will be randomly assigned depending on their geographical region:

- Patients aged ≥ 80 years old in the USA will be assigned to 110mg DE-DAT, 150mg DE-DAT or warfarin-TAT in a 1:1:1 ratio
- All other patients aged ≥ 80 years old (i.e. EU/ROW) will be assigned to 110mg DE-DAT or warfarin-TAT in a 1:1 ratio.

Patients will be randomised in permuted blocks, dynamically stratified by age (< 80 or ≥ 80 years old) and region (EU/ROW or USA) using an IRT. Dynamic stratification allocates blocks of randomisation numbers according to the strata of the first randomised patient within that block. For example, if the first patient randomised to the first block is < 80 years old and from the USA, other randomisation numbers within this block will only be allocated to patients < 80 years old from the USA (until there are no more randomisation numbers left to allocate within this block). BI will arrange for the packaging and labelling of study medication. The randomisation list will be generated using a validated system and a pseudo-random number generator so that the resulting treatment will be both reproducible and non-predictable. The block size will be documented in the CTR. Access to the codes will be controlled and documented.

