7.4 PRIMARY ENDPOINT

This is a prospective, randomised, open label, blinded endpoint (PROBE), active comparator trial and the clinical endpoints are being adjudicated by an IAC in a blinded fashion. The IAC

Charter contains details of the outcome event adjudication criteria. The study will employ a time to first event analysis (using a stratified Cox proportional hazards regression model) and it is assumed that all patients will be observed until first primary endpoint event or until the last patient entered has completed at least six months of treatment (up to an anticipated maximum duration of approximately 30 months for the first patient entered). The trial will be monitored by an independent DMC.

This study is designed to test two safety hypotheses in NVAf patients that have undergone a successful PCI (elective or due to ACS) with stenting and were treatment naïve or were receiving oral anticoagulant treatment (either with warfarin, another VKA or other novel oral anticoagulant) before the procedure.

The primary endpoint, measured from date of randomisation to end of observation period, is:

- Time to first ISTH MBE or CRNMBE

as determined by the IAC. Only positively adjudicated events will be included in the analyses. They will be analysed using the stratified Cox proportional hazards regression model including age group (non-elderly or elderly [<70 or ≥ 70 years old in Japan and <80 or ≥ 80 years old everywhere else]) as a stratifying factor and treatment arm (110mg DE-DAT vs warfarin-TAT and 150mg DE-DAT and 110mg DE-DAT combined vs warfarin-TAT). For the 150mg DE-DAT versus warfarin-TAT comparison, an unstratified model will be applied comparing 150mg DE-DAT versus warfarin-TAT (excluding elderly EU/ROW patients in the warfarin-TAT group). In addition, an unstratified sensitivity analysis of the non-elderly patients only will be conducted.

Models will be fitted for each comparison separately (110mg DE-DAT vs warfarin-TAT and 150mg DE-DAT vs warfarin-TAT). The Breslow method [9] will be used to handle tied failure times.

The primary analysis will be performed under the intention-to-treat framework on the FAS. Patients who discontinue study medication will be followed until the end of the trial for vital status, ECGs, AEs, OEs (including completion of the bleeding questionnaire) and concomitant medications. All patients will be analysed according to the treatment arm to which they were randomised.

Survival time

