7.5 SECONDARY ENDPOINTS

7.5.1 Key secondary endpoints

This section is not applicable as no key secondary endpoints have been specified in the protocol.

7.5.2 (Other) Secondary endpoints

Other secondary efficacy endpoints (all time to first event, measured from date of randomisation to end of observation period) are:

- A combined endpoint of DTE and unplanned revascularisation by PCI/CABG
- A combined endpoint of DTE
- Individual OEs:
 - All deaths
 - Cardiovascular death
 - Non-cardiovascular death
 - Undetermined
 - MI
 - Stroke
 - SE
 - Stent thrombosis (definite)

- Composite of death + MI + stroke
- Unplanned revascularisation by PCI/CABG

[figure not shown]
Time to first event endpoints will be analysed using the same methods as for the primary endpoint. However, comparisons will be for superiority of 110mg DE-DAT over warfarin-TAT, 150mg DE-DAT over warfarin-TAT and 150mg DE-DAT and 110mg DE-DAT combined over warfarin-TAT (for DTE/unplanned revascularisation and DTE, NI will be tested first). No multiplicity adjustments are planned for secondary endpoints, unless they are part of the hierarchical procedure (see [Section 7.4](#)). Nominal one-sided p-values will be reported for descriptive purposes. For analysis of stent thrombosis, Kaplan Meier plots will be provided additionally by stent type (DES, BMS,..) and by “Index PCI for ACS vs. elective index PCI (non-ACS)”.

Only positively adjudicated events will be included in the analyses. Secondary analyses will also include presentations of number (%) of patients with events.

All secondary analyses will be performed on the FAS. The robustness of these analyses will be assessed by on-treatment analyses of the TS.

Further sensitivity analyses will be performed on investigator reported events (i.e. those that are positively and negatively adjudicated). Post-treatment events will also be summarised and a summary of adjudication will be presented showing the number of investigator-reported OEs along with whether they were positively or negatively adjudicated or whether they were non-assessable.

Frequency counts will be provided showing the number of patients experiencing recurrent events by endpoint. The number of events will be presented as follows: the number of initial events, the number of additional events and the total number of events. Individual outcome events (with the exception of death), as described above, will be presented in these summaries.

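### The SAP drops age stratification for 150mg versus warfarin because the model supposedly cannot be fitted, which is incorrect, and the pooled-dose tests ignore that elderly allocation differs by region

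*SAP*

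**What the plan says.** Protocol 7.3.1 sets the primary model for both dose comparisons: "It will be analysed using the stratified Cox proportional hazards regression model including factors for age", with each comparison fitted separately. For 150mg versus warfarin, elderly EU/ROW patients are left out of the warfarin arm because none of them could be randomised to 150mg.

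SAP 4 withdraws this model for the 150mg comparison, for all endpoints, stating that "it will not be possible to fit an age-group stratified Cox proportional hazards regression model for the 150mg DE-DAT versus warfarin-TAT comparison". SAP 7.4 gives the replacement: "For the 150mg DE-DAT versus warfarin-TAT comparison, an unstratified model will be applied", again without elderly EU/ROW warfarin patients. SAP 4 adds a check: "In addition, unstratified sensitivity analyses of the non-elderly stratum only will be conducted". The change reaches the secondary endpoints through SAP 7.5.2: "Time to first event endpoints will be analysed using the same methods as for the primary endpoint".

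For the other two comparisons, SAP 7.4 uses age group "as a stratifying factor and treatment arm (110mg DE-DAT vs warfarin-TAT and 150mg DE-DAT and 110mg DE-DAT combined vs warfarin-TAT"). SAP 6.5 confirms that region is in no model.

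Protocol 7.5 randomises by age group and region. Elderly patients "in the USA will be assigned to 110mg DE-DAT, 150mg DE-DAT or warfarin-TAT in a 1:1:1 ratio", and all other elderly patients ("i.e. EU/ROW) will be assigned to 110mg DE-DAT or warfarin-TAT in a 1:1 ratio"). Non-elderly patients are 1:1:1 in both regions.

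**The concern.** There are two linked problems with the strata.

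**150mg versus warfarin (Steps 2 and 6).** A change to a confirmatory model needs a valid reason. This one appears in an SAP finalised on 9 June 2017, after the window for final visits (1 February to 30 April 2017), in an open-label trial. Nothing suggests that the choice was driven by results, but the technical ground given for it has to be true.

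**Pooled doses versus warfarin (Steps 3 and 5).** Combining the two dabigatran arms gives 2:1 allocation in elderly US patients and 1:1 in elderly EU/ROW patients, and both groups sit in one elderly stratum. Any difference in event risk between the US and elsewhere then enters the hazard ratio. If US risk is lower, the distortion favours dabigatran and makes non-inferiority easier to claim. The omission of region is inherited from the protocol model and is not an SAP deviation.

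**Working it through.** **The plan's own figure.** Inputs from Protocol 7.6: 334 events per pair of arms, margin 1.38, one-sided alpha 0.025. Power at a true HR of 1 is Φ(ln 1.38 × √334 / 2 − 1.960) = Φ(0.322 × 9.138 − 1.960) = Φ(0.983) = 83.7%, against the stated 83.6%. With 14% of patients having an event by one year, λ = −ln 0.86 = 0.1508 per year. With follow-up uniform over 6 to 30 months, P(event) = 0.1994, so 834 patients give 166 events per arm and about 499 in total. The plan's design figures reproduce and are used below.

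**Can the stratified model be fitted?** The log partial likelihood is a sum over strata of terms in one common coefficient β. A stratum with no events, or with patients in only one arm, contributes a constant. β is then estimated from the remaining strata.

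Assumed, because the documents do not give them: 760 non-elderly patients per arm, 15% of them US; elderly hazard ×2; US hazard ×1.5; and 1, 2, 5, 15 or 40 elderly US patients per arm. Datasets were simulated at true HR 1.0 and 1.38, with 2,000 per setting.

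- Failures of the stratified fit: 0 of 40,000. A cross-check in a standard package with Breslow ties, the SAP's method, gave 0 of 600.
- Elderly stratum with no events: stratified HR 0.9398, identical to the non-elderly-only fit.
- Elderly stratum in one arm only: stratified HR 0.9449, again identical to the non-elderly-only fit.

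**What does dropping age change for 150mg?** In the same simulations:

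| Elderly US per arm | NI power, unstratified | NI power, age-stratified |
|---|---|---|
| 1 | 82.4% | 82.2% |
| 5 | 85.2% | 85.2% |
| 40 | 86.1% | 85.7% |

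The mean shift in log HR was at most 0.0051, against ln 1.38 = 0.322. Standard errors differed by 0.0001 and type I error by at most 0.15 points. A further simulation with 10 elderly US patients per arm gave 80.6% power for both models.

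**The pooled tests.** Take 15 elderly US and 70 elderly EU/ROW patients per arm (assumed).

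- Warfarin: US share of the elderly = 15 / (15 + 70) = 17.6%.
- Dabigatran, both doses: 30 / (30 + 70) = 30.0%, since elderly EU/ROW patients enter only the 110mg arm.
- If the US hazard is ×1.5 and there is no treatment effect, the elderly hazards are in the ratio (1 + 0.300 × 0.5) / (1 + 0.176 × 0.5) = 1.150 / 1.088 = 1.057.
- If the US hazard is ×2/3, the ratio is 0.900 / 0.941 = 0.956.

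The non-elderly stratum dilutes this. The expected stratified score equation was solved at true HR 1, with 834 per arm (fewer on 150mg) and elderly hazard ×2. The 14% bleeding rate was borrowed because the documents give no DTE rate.

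| Elderly EU/ROW per arm | Elderly US per arm | Age-only HR, US ×1.5 | Age-only HR, US ×0.67 | Age × region HR |
|---|---|---|---|---|
| 70 | 5 | 1.003 | 0.997 | 1.000 |
| 70 | 15 | 1.008 | 0.994 | 1.000 |
| 150 | 5 | 1.003 | 0.997 | 1.000 |
| 150 | 15 | 1.008 | 0.993 | 1.000 |
| 150 | 40 | 1.018 | 0.985 | 1.000 |

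The standard error rises by at most 0.0004 under age × region strata (0.0930 to 0.0934 in the last row with US ×0.67).

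**Effect on error rate.** With SE 0.093, a pooled HR of 0.997 to 0.993 is a shift of 0.03 to 0.08 standard errors. The one-sided 2.5% then becomes Φ(−1.96 + 0.03) to Φ(−1.96 + 0.08), about 2.7% to 3.0%. In an extreme simulated case (20% elderly, US patients 40% of them, US hazard ×0.5), age-only strata gave 4.0% at true HR 1.38, with Monte Carlo error about 0.35 points.

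**The case against.** **The 150mg change has no inferential consequence.** Both retained cells are allocated 1:1, the unstratified model is valid, and the results barely move. The SAP discloses the change and plans a non-elderly-only check, which equals the stratified fit when there are no elderly events. For rare endpoints the stratified model may give elderly US patients no weight at all, while the unstratified model keeps them in the risk set. All of this stands, and it is why no bias is claimed. It does not rescue the stated reason: the protocol model can be fitted, so it should stay primary.

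**The pooled distortion rests on assumptions and is small.** The documents give no elderly US count, no US hazard and no DTE rate. At 5 to 15 elderly US patients per arm the shift is under 1%, and the 4.0% case sits badly with the SAP's own remark that such patients were few. This stands as a limit on size. SAP 6.5 also promises to look at consistency across regional subgroups, but that does not adjust Steps 3 and 5.

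**Japan.** The SAP counts Japanese patients aged 70 or over as elderly. Their allocation comes from a local amendment that is not among the documents. Treating them as 1:1 is an assumption, though it is consistent with their exclusion as elderly EU/ROW from the 150mg comparison.

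**Splitting the non-elderly by region is not needed**, since they are 2:1 in both regions. That is correct; it is unnecessary but harmless.

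**Conclusion.** The concern holds on both parts.

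For 150mg versus warfarin, the statement that the age-stratified model cannot be fitted is incorrect, and the protocol's model is set aside without need in two confirmatory steps and in every 150mg secondary analysis. This is an unjustified departure, not a demonstrated bias. The effect is at most 0.4 points of power and 0.15 points of type I error under the assumed recruitment and hazards.

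For the pooled tests, age-only strata leave an imbalance created by the randomisation scheme. It is probably below 1% on the hazard ratio if elderly US patients are as few as the SAP implies, and its direction depends on whether US risk is higher or lower. The 110mg comparison is unaffected, because allocation is 1:1 in every cell.

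This should be corrected, but it does not threaten the trial's conclusions by itself.

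**What to change.** In SAP 4 and 7.4:

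- Delete the claim that the model cannot be fitted, and keep the protocol's age-group stratification for 150mg versus warfarin, with strata non-elderly and elderly US.
- For the pooled-dose comparisons in Steps 3 and 5, stratify by the randomisation cells, age group × region. Three strata (non-elderly, elderly US, elderly EU/ROW) are enough to remove the imbalance.
- Leave the 110mg model as it is.
- Keep the unstratified and non-elderly-only 150mg fits, and an age-only pooled fit, as sensitivity analyses.

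The cost is one strata variable and revised wording, with no new data and no burden on patients. In simulation the 150mg change costs at most 0.4 points of power, and the pooled change adds at most 0.0004 to the standard error.

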For patients with DTEs and other OEs that include death (see [Section 7.5.2](#)), the date of death will not be used for censoring purposes, but instead will count as an event. In general, if the date last seen coincides with the date of any outcome event reported, this outcome event will be counted for the primary analysis.

These censoring rules determine the "time at risk" for counting of events for the primary analysis.

The robustness of the primary analysis will be assessed by an on-treatment analysis of the TS and the PPS. The same censoring rules as defined above will be used. However, for patients who already had their EOT visit (i.e. those who stopped treatment prematurely), they will be censored at the date of their last trial medication intake plus 6 days. It will also analyse patients by the actual treatment taken.

The censoring rules defined for the on-treatment analysis determine the "time at risk" for counting of events for the on-treatment analysis, i.e. the on-treatment analysis will only count events that occur while a patient is taking study medication (+ REP of 6 days, if study

medication is stopped prematurely before study end). The date of first intake of study medication will be used as the start of the analysis period in this analysis instead of the date of randomisation. Intermittent off-treatment periods will be ignored in cases of any temporary interruptions in study medication.

These analyses will be based on the TS and the on-treatment period.

The proportional hazards assumption will be investigated for the primary analysis only. The following techniques will be used:

- Plotting log (-log (survival function)) against the log of time by treatment group. Parallel curves are consistent with the proportional hazards assumption.

- Adding time-dependent variables to the Cox model
For each variable in the model an interaction term is derived by multiplying by the log of time and adding to the model. Non-significance at the 5% level is consistent with the proportional hazards assumption.

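### SAP 4 cancels the protocol's crossover sensitivity analysis after misdescribing it, and the reason it gives does not apply to the analysis the protocol planned

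*SAP*

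**What the plan says.** Protocol 7.3.1 gives two robustness checks on the primary endpoint. The first is an on-treatment analysis. The second is listed as additional to it and "censors patients who switch from dabigatran to non-study warfarin or from study warfarin to non-study NOAC, at the time of the switch". No residual-effect period is added, and switches within a class are not mentioned.

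SAP 4 reports that a crossover analysis will not be run, and describes it as censoring patients who "switch from study dabigatran to non-study NOAC/VKA or from study warfarin to non-study NOAC/VKA, at the time of the switch", plus the 6-day residual effect period. Its reason is that the analysis is dropped "because it will be virtually identical to the on-treatment sensitivity analysis already planned".

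The on-treatment analysis in SAP 7.4 is based on the Treated Set. For patients who stopped study drug prematurely, "they will be censored at the date of their last trial medication intake plus 6 days". Its clock differs from that of the primary analysis: "The date of first intake of study medication will be used as the start of the analysis period in this analysis". On grouping: "It will also analyse patients by the actual treatment taken".

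For the main result, SAP 7.4 says: "The primary analysis will be performed under the intention-to-treat framework on the FAS". Under Protocol 6.2.2, patients who stop treatment are followed to the end of the study, so first events after a switch count in the primary analysis.

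**The concern.** The analysis cancelled in SAP 4 is not the one planned in the protocol. It differs in the drugs that define a switch, in the patients censored and in the censoring date. A finding of near-identity for the SAP's version says nothing about the protocol's.

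This matters because the primary hypotheses are non-inferiority hypotheses. If dabigatran dual therapy were truly worse for bleeding, time spent on the other class would pull the intention-to-treat HR towards 1, which favours the claim. Some crossover is foreseeable. The trial is open label, Protocol Appendix 10.2 expects most patients who stop to need further anticoagulation, and the rationale for global amendment 2 records that patients already treated with NOACs were unwilling to be randomised to warfarin.

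If the intention-to-treat and on-treatment results diverged, a reader would want to know whether class crossover or discontinuation in general was responsible. The protocol's analysis is the one that addresses that question.

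**Working it through.** **1. The three analyses side by side**

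| Feature | Protocol 7.3.1 switch analysis | Switch analysis cancelled in SAP 4 | SAP 7.4 on-treatment |
|---|---|---|---|
| Who is censored early | Dabigatran to non-study warfarin; study warfarin to non-study NOAC | Either study drug to any non-study NOAC or VKA | Every premature stopper |
| When | At the switch | Switch + 6 days | Last intake + 6 days |
| Dabigatran patient moves to a NOAC | Kept | Censored | Censored |
| Warfarin patient moves to another VKA | Kept | Censored | Censored |
| Patient stops and takes no anticoagulant | Kept | Kept | Censored |
| Set, origin, grouping | Not stated | Not stated | Treated Set, first intake, actual treatment |

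The second and third columns are close if nearly all stoppers go on to another anticoagulant. The first and third censor the same patients only if every stopper changes class.

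**2. The plan's own figure**

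Inputs from Protocol 7.2 and 7.6: margin 1.38, one-sided alpha 0.025, 334 events per pair, stated power 83.6%.

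- SE of log HR = 2/√334 = 0.1094.
- Power = Φ(ln 1.38/0.1094 − 1.96) = Φ(2.943 − 1.96) = 83.7%.

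The design figure reproduces and is not in dispute.

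**3. Dilution, as an illustration**

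Assumptions not in the documents: the true HR equals the margin, a share c of patient-time in each arm is spent on the other class, and that time carries the full hazard of the opposite arm.

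- HR_ITT = [(1−c)·1.38 + c] / [(1−c) + 1.38c]
- False non-inferiority rate = Φ((ln 1.38 − ln HR_ITT)/0.1094 − 1.96)

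| c | HR_ITT | False non-inferiority rate |
|---|---|---|
| 0 | 1.38 | 2.5% |
| 5% | 1.336 | 4.8% |
| 10% | 1.293 | 8.6% |
| 15% | 1.252 | 14.3% |

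If crossing transfers only half the effect, crossed time has relative hazard 1.19 in both arms. At c = 5% the HR is (0.95·1.38 + 0.05·1.19)/(0.95 + 0.05·1.19) = 1.3705/1.0095 = 1.358, and the rate is 3.5%. The same step gives 4.8% at c = 10% and 6.5% at c = 15%.

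**4. Information kept, as an illustration**

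Assume 20% of the 334 events fall after study drug is stopped.

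- On-treatment keeps 334 × 0.80 = 267 events (power 74.9%).
- Censoring only class-changers keeps 334 × (1 − 0.20x) events, where x is their share of those late events: 317, 301 or 284 for x = 25%, 50% or 75% (power 81.8%, 79.7%, 77.4%).
- At x = 100% both analyses keep 267.

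**The case against.** The case for leaving the SAP as it stands is substantial.

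- **Crossover is already covered in part.** A reader might infer that the trial has no check on crossover dilution. It has: on-treatment removes essentially all post-switch time, and the per-protocol analysis adds to that, although SAP 6.3 lets it be skipped if under 10% of the Treated Set is excluded. This stands. What is lost is a narrower analysis that isolates one cause.
- **Informative censoring.** A reader might infer that on-treatment is badly biased because bleeding prompts patients to stop. Protocol 5.2.2.1 largely answers this: an overt non-major bleed that leads the physician to change or stop study drug is itself a primary event, so many such patients have an event and are not censored. Stops for frailty or other illness remain, but they can affect the crossover analysis too.
- **The error rates.** A reader might take 4.8% to 14.3% as estimates for this trial, or think the extra analysis would bring them down. Neither holds. No switching rate is given, and the rate belongs to the primary test, which a sensitivity analysis leaves unchanged. The randomised contrast is also dual versus triple therapy, with aspirin for one or three months in the warfarin arm, so a dabigatran patient who moves to a VKA does not thereby receive the full comparator regimen.
- **Near-identity may hold in one arm.** Both exit routes described in Appendix 10.2 take dabigatran patients to warfarin or another VKA, which is a class change. That supports the SAP's reasoning for those patients, but the appendix says it does not list every approach, and it does not settle the warfarin arm.
- **Disclosure.** The cancellation is stated openly with a reason, so nothing suggests concealment.

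None of this makes the SAP's description match the protocol's analysis, or its reason apply to it.

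**Conclusion.** The point holds as a documentation and sensitivity-analysis fault, and should be corrected. SAP 4 cancels a pre-specified analysis on a ground that fits only a redefined version of it. No visible analysis of the primary endpoint separates change of drug class from other discontinuation. SAP 5.3, 6.4 and 7.6 are not visible, but SAP 4 says plainly that the analysis will not be performed.

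The size of any dilution is unknown. The range of 4.8% to 14.3% is an upper-end illustration: it assumes a true HR at the margin, 334 events, 5% to 15% crossed time in both arms, and full transfer of the opposite arm's hazard. With half transfer it is 3.5% to 6.5%. The documents do not support a claim that the primary analysis is invalid or its conclusion unsafe.

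**What to change.** Delete the last paragraph of SAP 4 and reinstate the Protocol 7.3.1 analysis in SAP 7.4, labelled supportive, for 110mg and for 150mg DE-DAT against warfarin-TAT. Specify:

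- Full Analysis Set, time from randomisation, randomised groups. The protocol does not state these for the switch analysis; this choice matches the primary analysis.
- Censoring only at a between-class switch, on the date of the switch. Say how that date is set when the old and new drug overlap, since Appendix 10.2 allows 2-3 days of overlap, and whether a VKA other than warfarin counts.
- A table of the number, type (between-class, within-class, no further anticoagulant) and timing of switches by arm.

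Keep the on-treatment and per-protocol analyses as they are. If the sponsor still prefers to drop the analysis, SAP 4 should at least describe the protocol's version correctly and justify dropping that version.

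The cost is one Cox model per comparison and one table. Non-study VKA and NOAC use is already recorded in detail (Protocol 4.2) and summarised by category (SAP 7.2). The drawback is that censoring at crossover may itself be informative, so the result can support the primary analysis but not replace it.
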